### Derived Visit Windowing Rule for ACR Response Calculation

To identify the component value in a visit window:

- ACR component values will first be determined at each date within a visit window.

- ACR component values at each date will be combined to determine the "as observed" ACR composite score at each date in each window.
- After this calculation, if multiple non-missing ACR composite scores are available within a given visit window, the non-missing ACR composite score closest to the target day will be used. If two composite scores have the same distance from the target day, the later one will be used. The corresponding date will be used as the "as observed" ACR response date in the derived efficacy dataset.
- If a non-missing ACR composite score is not available for any day within a given visit window, the windowed component values for that visit will be used to calculate the ACR composite score for that visit window (component value windowing follow the same rules as in steps described above). The date of observed ACR composite score will be determined by the first available ACR component date, in the order of TJC, SJC, Pain, PGA, PhGA, HAQ-DI, CRP/ESR, in the derived efficacy dataset.

### 10.7.2 Joint Evaluation

Anatomical joints are evaluated for swelling and tenderness at every study visit. The 34 anatomical joints in [Table 9](#) are assessed in this study for both the left and right side of the body.

**Table 9. Anatomical Joints Assessed for Calculation of Tender and Swollen Joint Counts (TJC68 and SJC66)**

Temporomandibular	Sternoclavicular	Acromio-clavicular	Shoulder
Elbow	Wrist	Metacarpophalangeal I	Metacarpophalangeal II
Metacarpophalangeal III	Metacarpophalangeal IV	Metacarpophalangeal V	Interphalangeal Thumb Joint
Proximal Interphalangeal Joint II of the Hand	Proximal Interphalangeal Joint III of the Hand	Proximal Interphalangeal Joint IV of the Hand	Proximal Interphalangeal Joint V of the Hand
Distal Interphalangeal Joint II of the Hand	Distal Interphalangeal Joint III of the Hand	Distal Interphalangeal Joint IV of the Hand	Distal Interphalangeal Joint V of the Hand
Hip a	Knee	Ankle	Transverse Tarsus
Metatarsophalangeal I	Metatarsophalangeal II	Metatarsophalangeal III	Metatarsophalangeal IV
Metatarsophalangeal V	Interphalangeal Joint I of the Foot	Proximal Interphalangeal Joint II of the Foot	Proximal Interphalangeal Joint III of the Foot
Proximal Interphalangeal Joint IV of the Foot	Proximal Interphalangeal Joint V of the Foot		

a. Hip joints are not assessed for swelling.

At each study visit, a joint evaluator assessed whether a particular joint was "tender or painful" where presence of tenderness was scored as "1" and the absence of tenderness was scored as "0." The total tender joint count (TJC68), which is based on 68 joints, will be derived as the sum of all "1"s and proportional extrapolation will be used to compute joint counts for the joints that are replaced or not assessed. A similar method will be followed for the derivation of total swollen joint count (SJC66), which is based on 66 joints as the hip joints are excluded. Thus, the range for TJC68 will be 0 to 68 and 0 to 66 for SJC66. Joints with surgery (e.g., joint replacement) will not be assessed.

#### **10.7.3 Patient's Global Assessment of Disease Activity Visual Analog Scale (VAS)**

The patient's global assessment of disease activity will be performed using a horizontal 100 mm VAS, ranging from 0 (very well) to 100 (very poor) after the question:

"Considering all the ways psoriatic arthritis affects you, please indicate with a vertical mark ( | ) through the horizontal line how well you are doing today."

#### **10.7.4 Physician's Global Assessment of Disease Activity Visual Analog Scale (VAS)**

The physician will assess Patient's disease activity at the time of visit using a physician's Global Assessment of Disease VAS. The range is 0 to 100 mm with no activity being indicated by 0 and severe activity by 100.

#### **10.7.5 Patient's Global Assessment of Pain**

The patient's assessment of pain will be performed using a horizontal 100 mm visual analog scale (VAS), ranging from 0 (no pain) to 100 (severe pain) after the question:

"Please indicate with a vertical mark ( | ) through the horizontal line the most pain you had from your psoriatic arthritis today."

#### **10.7.6 Disease Activity Score Based on DAS28 (hsCRP)**

The Disease Activity Score (DAS) is a combined index used to measure the disease activity in patients with PsA. The DAS provides a score between 0 and 10, indicating how active the joint disease in Psoriatic Arthritis is at the time of measurement. DAS28 (hsCRP) score will be determined based on a continuous scale of combined measures of TJC, SJC, Patient Global Assessment of Disease Activity (PtGA) (in mm), and hsCRP (in mg/L).

$$\text{DAS28 (hsCRP)} = 0.56 \sqrt{(\text{TJC28})} + 0.28 \sqrt{(\text{SJC28})} + 0.36 \ln(\text{hsCRP} + 1) + 0.014 \text{PtGA} + 0.96$$

where  $\sqrt{}$  is square root and  $\ln$  is natural log. A score  $> 5.1$  generally means high disease activity;  $2.6 \leq \text{DAS28 (hsCRP)} < 3.2$  generally means low disease activity (LDA);  $\text{DAS28 (hsCRP)} < 2.6$  is generally considered clinical remission (CR).

**Table 10. Anatomical Joints for DAS28 (hsCRP) Calculation**

Shoulder	Elbow	Wrist	Thumb Interphalangeal
Metacarpophalangeal I	Metacarpophalangeal II	Metacarpophalangeal III	Metacarpophalangeal IV
Metacarpophalangeal V	Proximal Interphalangeal II	Proximal Interphalangeal III	Proximal Interphalangeal IV
Proximal Interphalangeal V	Knee		

#### **10.7.7 Health Assessment Questionnaire – Disability Index (HAQ-DI)**

HAQ-DI is a self-reported patient outcome measurement tool commonly used in RA and PsA clinical trials to measure physical functioning in RA and PsA patients. The HAQ-DI composite score is calculated as the mean of the scores from the 8 following categories with a range of 0 – 3 (0 = no disability; 3 = worst disability): Dressing and Grooming, Rising, Eating, Walking, Hygiene, Reach, Grip, and Activities. The higher the score, the more likely to be associated with morbidity and mortality for the PsA patient. Under each category there are 2 – 3 items on the amount of difficulty they have in performing specific activities with four response options from 0 (no difficulty) to 3 (unable to do). In addition to these eight categories, there is an aids or devices/help from other person section ("companion items") that is used to record the type of assistance, if any, a subject uses for his/her usual activities in each of the eight categories.

The preferred and traditional scoring method for scoring HAQ-DI is the Standard HAQ-DI approach which takes into account the use of the aids/devices section. There are three steps to compute the HAQ-DI score and a patient must have a score for at least six of the eight categories, otherwise a HAQ-DI score cannot be computed. The first step is to compute each of the category score. The maximum score for all the questions in each category is considered as the score for the category. The second step is to adjust the score of each category based on use or no use of aids/devices and/or help from another person when indicated. If aids or devices and/or assistance from another person are

checked for a disability category, and the score for the category is 0 (no difficulty) or 1 (some difficulty), increase it to 2 (much difficulty). If the score for the category is a 2, it remains a 2, and if it is a 3, it remains a 3. The third step is to sum the adjusted categories scores and divide by the number of categories answered (minimum 6) to obtain a HAQ-DI score of 0 to 3.

[figure not shown]
#### **10.7.8 SF-36v2 (Acute Form)**

The 36-Item Short Form, Version 2 (SF-36v2) Questionnaire with 1 week recall consists of 36 general health questions and this study is using the form for 4 weeks recall period (standard form). It has 2 components: physical and mental. For each component, a transformed summary score is calculated using 8 subdomains: physical functioning, role-physical, bodily pain, general health, vitality, social functioning, role-emotional, and mental health.

The coding and scoring for the SF-36 will use the software provided by Optimum.

Changes from baseline for each component and each of the 8 subdomains will be summarized by visit and treatment group. Analysis will be based on Observed Case only.

Spydergrams will be plotted for the 8 sub-domains of SF-36v2. In a spydergram, physical function (PF) is at the top, 12 o'clock, followed clockwise by role physical (RP), bodily pain (BP) and general health perceptions (GH), and vitality (VT) at the 6 o'clock position, followed by social functioning (SF), role emotional (RE) and mental health index (MH) clockwise ([Figure 2](#)). Domain scores are plotted from 0 (worst) at the center to 100 (best) at the outside; demarcations along axes of the domains present changes of 10 points, representing one to two times minimally clinical important differences (MCID). An example of a spydergram is shown below. The spydergram is a radar chart that can be plotted using PROC GRADAR in SAS version 9.4.

**Figure 2.** An Example of Spydergram of SF-36

Note: Strand 2009.

### 10.7.9 Psoriasis Area and Severity Index (PASI)

Four anatomic sites – head, upper extremities, trunk, and lower extremities – are assessed for erythema, induration and desquamation using a 5-point scale:

- 0 = no symptoms
- 1 = slight
- 2 = moderate
- 3 = marked
- 4 = very marked

Based on the extent of lesions in a given anatomic site, the area affected is assigned a numerical value:

- 1 = < 10%
- 2 = 10% – 29%

---

- 3 = 30% – 49%
- 4 = 50% – 69%
- 5 = 70% – 89%
- 6 = 90% – 100%

Since the head, upper extremities, trunk and lower extremities correspond to approximately 10, 20, 30 and 40% of body surface area, respectively; the PASI score is calculated using the formula:

$$\text{PASI} = 0.1(E_h + I_h + D_h)A_h + 0.2(E_u + I_u + D_u)A_u + 0.3(E_t + I_t + D_t)A_t + 0.4(E_l + I_l + D_l)A_l$$

where  $E$ ,  $I$ ,  $D$ , and  $A$  denote erythema, induration, desquamation, and area, respectively, and  $h$ ,  $u$ ,  $t$ , and  $l$  denote head, upper extremities, trunk, and lower extremities, respectively. PASI scores range from 0.0 to 72.0 with the highest score representing complete erythroderma of the severest possible degree. Typically scores of 3 or less represent mild disease, scores over 3 and up and including 15 represent moderate disease and scores over 15 are considered to be associated with severe disease.

The frequency and percentage of PASI/75/90/100 (defined as 75%, 90% and 100% improvement in PASI score compared to baseline) will be summarized by treatment group in subjects with  $\geq 3\%$  BSA (Body Surface Area) psoriasis involvement at baseline.

BSA will be approximated by the following formula using the affected area information (lower bound of each degree) collected for PASI.

$$\text{BSA} = 0.1*\text{Lower}(\text{Area\_h}) + 0.2*\text{Lower}(\text{Area\_u}) + 0.3*\text{Lower}(\text{Area\_t}) + 0.4*\text{Lower}(\text{Area\_l})$$

where  $\text{Lower}()$  takes the lower bound percentage corresponding to the affected area score. For example, if  $\text{Area\_h} = 1$ , then  $\text{Lower}(\text{Area\_h}) = 0\%$ . If  $\text{Area\_h} = 5$ , then  $\text{Lower}(\text{Area\_h}) = 70\%$ .

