5.3.3.3 Further Endpoint(s)

Further efficacy endpoints will include, but are not limited to, the following:

- ACR 50 at all measured time points
- ACR 70 at all measured time points
- Change in Tender Joint Count at all measured time points as compared to baseline
- Change in Swollen Joint Count at all measured time points as compared to baseline
- Change in HAQ-DI at all measured time points as compared to baseline
- Change in SF-36 at all measured time points as compared to baseline

- Change in Dactylitis count at all measured time points as compared to baseline
- Change in SPARCC Enthesitis Index at all measured time points as compared to baseline
- Change in mNAPSI at all measured time points as compared to baseline
- Change in PhGA (VAS) at all measured time points as compared to baseline
- Change in Patient's Assessment of PsA Pain Intensity (VAS) at all measured time points as compared to baseline
- Change in PtGA assessments at all measured time points as compared to baseline
- Change in High sensitivity C-Reactive Protein (hsCRP) at all measured time points as compared to baseline
- Minimal disease activity (MDA) at all measured time points
- Change in DAS28-hsCRP at all measured time points as compared to baseline
- PsO endpoints assessed at all measured time points in subjects with a $\geq 3\%$ baseline PsO BSA:
 - PASI 75 and PASI 90 response
 - Change in sPGA clear and almost clear
- EULAR (European League Against Rheumatism) response at all measured time points
- Change in PsARC (Psoriatic Arthritis Response Criteria) at all measured time points as compared to baseline
- Presence of dactylitis (yes/no) at all measured time points
- Change in LDI at all measured time points as compared to baseline
- Change in LEI at all measured time points as compared to baseline
- Change in FACIT-F at all measured time points as compared to baseline
- Change in BASDAI at all measured time points (in subjects with baseline inflammatory spondylitis, based on investigator judgment, in Study 1311.5) as compared to baseline

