10.0 Source Documents and Case Report Form Completion

10.1 Source Documents

Source documents are defined as original documents, data and records. This may include hospital records, clinical and office charts, laboratory data/information, subjects' diaries or evaluation checklists, pharmacy dispensing and other records, recorded data from automated instruments, microfiches, photographic negatives, microfilm or magnetic media, and/or x-rays. Data collected during this study must be recorded on the appropriate source documents.

Due to the nature of an open label extension study, data that is common to both Study 1311.5 and Study M16-244 studies may be shared. AbbVie will provide instruction regarding entry of this data.

The investigator(s)/institution(s) will permit study-related monitoring, audits, IEC/IRB review, and regulatory inspection(s), providing direct access to source data documents.

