- r. Required at EOS visit only for subjects that prematurely discontinue prior to Week 24 visit.
- s. For subjects that prematurely discontinue, study drug will not be given at the early EOT visit.
- t. At Week 4 visit, if the additional dose is not administered all other referenced procedures will be completed during this visit.

- u. PASI and sPGA are assessed in patients with $\geq 3\%$ BSA of psoriatic plaques at baseline in Study 1311.5 and/or current visit.
- v. Subject to attend study visits in a fasted state (8 hours no food and only water). If a patient comes in non-fasted where a fasting condition is required, the visit should be performed, and the non-fasted condition documented on the laboratory requisition.

See [Appendix D](#) for Japan specific requirements.

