## **6.4                   Definition of Analysis Windows**

All time points and corresponding time windows are defined based on Rx Days.

For efficacy analyses, laboratory parameters, and vital sign variables, analysis windows are constructed using the following algorithm:

- Determine the nominal Rx day for each visit (e.g., Week 4 [4 weeks after Baseline visit] equals Rx Day 29).
- In order to include all post baseline data, the first post-baseline interval starts on the first day after the first dose of study drug (Rx Day 2).

---

- Determine the window around a specific nominal Rx day by adding or subtracting half of the interval between adjacent visits (e.g., days between Week 2 and Week 4 is 14). The threshold between adjacent visits is determined by splitting the interval evenly between the visits. If the resulting split is between Rx days, then the threshold is determined as the midpoint between the adjacent visits. If the resulting split is on a Rx day, then the threshold is determined as being between that Rx day and the Rx day prior to it (e.g., the split between Week 2 and Week 4 would be between Rx Days 22 and 23).
- If more than one assessment is included in a time window the assessment closest to the nominal day will be used. If there are two observations equidistant to the nominal day, the one after the nominal day will be used in analyses. If more than one assessment is included on the same day, then the worst assessment on that day will be used in analyses. For laboratory values, if there are multiple measurements on the same day, average value will be used.

The protocol specified visits and corresponding time windows used in the various efficacy analyses, laboratory parameters, and vital sign variables, are presented in the following tables.

**Table 1. Analysis Windows for Efficacy Variables (PtGA, Patient's Assessment of PsA Pain Intensity, HAQ-DI, SF-36v2, TJC68, SJC66, PASI, BSA, sPGA, PhGA, hsCRP for DAS)**

Protocol Specified Visit Week	Lower Bound	Target Day	Upper Bound
0	1	1	1
4	2	29	57
12	58	85	127
24	128	169	211
36	212	253	295
48	296	337	351
52	352	365	378

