### **PsA Medical History and Disease Characteristics at Baseline**

- Categorical:
  - MDA (Minimal Disease Activity) for PsA
  - sPGA (Static Physician Global Assessment) assessed in subjects with ≥ 3% BSA of psoriatic plaques
  - Presence of Dactylitis (yes/no)
  - Presence of Enthesitis based on LEI (yes/no)
  - Presence of Enthesitis based on SPARCC (yes/no)
  - Presence of nail psoriasis (yes/no)
  - Body Surface Area (BSA) of psoriatic plaques: ≥ 3% vs < 3%
  - Prior exposure to TNF antagonists (TNFi's; Experienced versus Naive)
  - Concurrent exposure to Methotrexate (Concurrent use versus Non-concurrent use)
  - Presence of inflammatory spondylitis (yes/no)
  - Duration of PsA Categories (≤ 5, [5, 10], > 10)
  - Rheumatoid Factor (RF) status: Positive (≥ 15) or Negative (< 15)
- Continuous
  - PASI (Psoriasis Area and Severity Index) assessed in subjects with ≥ 3% BSA of psoriatic plaques
  - DAS28 (Disease Activity Score in 28 joints) – hsCRP
  - Dactylitis count in subjects with dactylitis at baseline 0 – 20
  - Leeds Dactylitis Index (LDI) in subjects with dactylitis at baseline
  - Leeds Enthesitis Index (LEI) in subjects with enthesitis (based on LEI) at baseline (yes/no) 0 – 6
  - Duration since diagnosis of PsA in years

- CASPAR classification criteria total score
- SPARCC (Spondyloarthritis Research Consortium of Canada) Enthesitis Index in subjects with enthesitis (based on SPARCC) at baseline (yes/no) 0 – 16
- mNAPSI (Modified Nail Psoriasis Severity Index) assessed in subjects with nail psoriasis at baseline 0 – 130

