**Table 8. Summary of Efficacy Variables and Corresponding Analyses**

Efficacy Variables	Summary Method
Categorical Efficacy Endpoints:	
Secondary Binary Endpoint: ACR20 responses at all measured time points	
 
• Point estimates and 95% CIs of the response rates
 
• Imputation: OC
 

Other Categorical Endpoints: At all measured time points:	
 
• Point estimates and 95% CIs of the response rates
 
• Imputation: OC
 

 
• ACR50
 
• ACR70
 
• Minimal disease activity (MDA)
 
• PASI75 response in subjects with a <math>\geq 3\%</math> baseline PsO BSA
 
• PASI90 response in subjects with a <math>\geq 3\%</math> baseline PsO BSA
 
• PASI100 response in subjects with a <math>\geq 3\%</math> baseline PsO BSA
 
• sPGA clear and almost clear in subjects with a <math>\geq 3</math> baseline PsO BSA
 
• Psoriatic Arthritis Response Criteria (PsARC)
 
• European League Against Rheumatism (EULAR) Response
 
• Presence of dactylitis (yes/no)
 
• No Progression of mTSS
 
	
Continuous Efficacy Endpoints	
Secondary Continuous Endpoint: Change from baseline in Study 1311.5 at Week 24 (Study 1311.5), Week 24 (Study M16-244) and Week 48:	
 
• Point estimates, 95% CIs of mean change from baseline together with SD, Min, Q1, Median, Q3 and Max
 
• Imputation: OC
 

Change from baseline in Study M16-244 at all measured timepoints:	
 
• mTSS
 
• HAQ-DI
 
• SF-36
 

**Table 8.****Summary of Efficacy Variables and Corresponding Analyses  
(Continued)**

Other Continuous Endpoints:	
At all measure time points as compared to baseline in Study M16-244:	

• Point estimates, 95% CIs of mean change from baseline together with SD, Min, Q1, Median, Q3 and Max

• For SF-36, spyderdiagram will be provided

• Imputation: OC

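### SAP 10.7.9 derives BSA from the lower bound of each PASI area band, which can only shrink the ≥3% BSA population used for PASI75/90/100

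*SAP*

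**What the plan says.** SAP 10.7.9 restricts the PASI75/90/100 summaries to subjects with at least 3% BSA at baseline. The next paragraph states: "BSA will be approximated by the following formula using the affected area information (lower bound of each degree) collected for PASI". The formula weights head, upper extremities, trunk and lower extremities by 0.1, 0.2, 0.3 and 0.4. Its worked examples give 0% for area score 1 and 70% for area score 5. There is no exception for the 3% cut-off, and a recorded BSA is not given precedence.

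Other places bear on this:

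- Protocol 5.3.3.3 defines the population with no approximation: "PsO endpoints assessed at all measured time points in subjects with a" baseline psoriasis BSA of at least 3%.
- SAP Table 8 applies the same threshold to sPGA ("sPGA clear and almost clear in subjects with a" baseline BSA at that level). SAP 7.1 has a baseline row for "Body Surface Area (BSA) of psoriatic plaques" split at 3%.
- BSA has its own row in the Protocol Appendix C schedule for M16-244 visits. It is also a windowed variable in its own right in SAP Table 1: "TJC68, SJC66, PASI, BSA, sPGA, PhGA, hsCRP for DAS".
- Footnote u of Appendix C requires PASI and sPGA in subjects with at least 3% "BSA of psoriatic plaques at baseline in Study 1311.5 and/or current visit".

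**The concern.** A PASI area score does not resolve anything below 10% of a region, yet here it is used to apply a 3% whole-body cut-off. Taking the bottom of each band pushes every error the same way. Followed literally, the rule can drop subjects whose skin disease meets the protocol's criterion from the PASI75/90/100 denominators. It can also give a subject a BSA of zero alongside a PASI well above zero.

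The sPGA population and the baseline ≥3% versus <3% row use the same threshold, and the SAP gives no other definition of BSA. It is an inference, but a natural one, that a programmer would use the same derived value there. The retained group would then tend towards more extensive skin involvement than the protocol population.

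**Working it through.** **Inputs.** Weights: 0.1 head, 0.2 arms, 0.3 trunk, 0.4 legs (SAP 10.7.9). Bands for scores 0 to 6: none, <10, 10 to <30, 30 to <50, 50 to <70, 70 to <90, 90 to 100% (Protocol Appendix F; the SAP prints the same bands with tops of 29, 49 and so on). Lower bounds: 0, 0, 10, 30, 50, 70, 90%. Cut-off: 3%. The weights and bands are taken as exact.

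**The SAP's own figures.** Lower(1) = 0% and Lower(5) = 70%, as printed.

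**Direction of error.** In each region the lower bound is no greater than the true involvement, so the weighted sum is no greater than the true BSA. False inclusion at ≥3% is impossible; false exclusion is not.

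**What it takes to reach a derived 3%.** Contributions to derived BSA by score:

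| Region | Score 0 or 1 | Score 2 | Score 3 |
|---|---|---|---|
| Head | 0 | 1% | 3% |
| Arms | 0 | 2% | 6% |
| Trunk | 0 | 3% | 9% |
| Legs | 0 | 4% | 12% |

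So a subject needs score ≥2 in trunk or legs, or ≥3 in head or arms, or ≥2 in both head and arms.

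**Patterns.** There are 7⁴ = 2401. Derived BSA is below 3% when trunk and legs are each 0 or 1, and head and arms are each 0 to 2 but not both 2: 2 × 2 × (9 − 1) = 32. Six of these cannot hold a true BSA of 3% or more: no involvement; head 1; head 2; arms 1; trunk 1; head 1 with arms 1. The other 32 − 6 = **26** can. The highest limit is head 1, arms 2, trunk 1, legs 1: 0.1×10 + 0.2×30 + 0.3×10 + 0.4×10 = 14% (not attained), against a derived 2%. With the SAP's printed band tops the count is still 26 and the limit is 13.8%.

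All 2⁴ = 16 patterns made only of scores 0 and 1 give a derived 0%, and 11 of them allow a true BSA of 3% or more.

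**Individual examples.**

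- Trunk 9% and legs 9%: true 0.3×9 + 0.4×9 = 6.3%; derived 0%.
- Legs alone 8%: true 0.4×8 = 3.2%; derived 0%.
- Score 1 in all four regions with erythema, induration and desquamation each 2: PASI = (0.1 + 0.2 + 0.3 + 0.4) × 6 × 1 = 6.0, which SAP 10.7.9 calls moderate disease; derived BSA 0%.

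**Even involvement.** To see whether this needs contrived patterns, suppose the affected regions are evenly involved. Of the 15 non-empty combinations of regions, 12 have a range of true BSA that is misclassified; head alone, trunk alone and head with arms do not. The range is 3 to <10% for all four regions, 3 to <7% for trunk with legs, and 3 to <4% for legs alone.

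**MDA skin item (conditional).** SAP 10.7.12 accepts PASI ≤1 or BSA ≤3 without naming the BSA source. If the derived value were used, the item could be falsely met when PASI is above 1 and true BSA is above 3%. Under the rule of ≥5 met for a responder and ≥3 unmet for a non-responder, this changes the result in 7 of the 28 met/unmet/missing splits of the other six items. In three of these, exactly four are met and the subject becomes a responder. In the other four, exactly two are unmet and at most three met, and a non-responder becomes undetermined.

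**The case against.** The strongest reply is that the formula was perhaps never meant to override a site determination. SAP 7.1 describes baseline "PASI (Psoriasis Area and Severity Index) assessed in subjects with" at least 3% BSA, which suggests that sites set the class before scoring PASI. On that view the gap is only that the BSA source is unstated, and the extension to sPGA and the baseline row is inference. The inference point is fair. But 10.7.9 places the formula directly after the ≥3% restriction with no exception, so a programmer following it would build the narrower population.

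Second, the cut-off belongs to Study 1311.5, and nothing shows that a numeric baseline BSA was recorded there or transferred. Appendix C and Table 1 cover M16-244 visits only. This stands and has to be checked. Footnote u does imply that sites need the baseline ≥3% class, and Protocol 10.1 says "data that is common to both Study 1311.5 and Study M16-244 studies may be shared". If neither the value nor the class can be obtained, the fallback keeps the misclassification.

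Third, patterns are neither subjects nor equally likely, and 14% is a corner case. Agreed; the even-involvement ranges are the fairer guide. The skew towards extensive disease is also only a tendency: 29% of the arms (0.2×29 = 5.8%) is excluded, while 10% of the trunk (3.0%) is kept.

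Finally, the study is single-arm and descriptive, and PASI and sPGA are further endpoints. That limits the importance of the point but does not make the rule right.

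**Conclusion.** The concern holds. As written, 10.7.9 can remove subjects with qualifying skin disease from the PASI75/90/100 denominators and can never add anyone wrongly, given the SAP's own weights and bands. Twenty-six of the 32 patterns classed below 3% are compatible with a true BSA of 3% or more, and ordinary evenly spread disease is enough to trigger the error.

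The number of subjects affected, and the size and direction of any change in response rates, cannot be derived from the documents. The reach to sPGA and the baseline row rests on the shared threshold, and the MDA effect arises only if the derived value is used there. No primary or secondary result changes. It should still be fixed, because the stated rule produces a different population from the one the protocol defines.

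**What to change.** Name the BSA source for each use:

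- **PASI and sPGA populations and the baseline ≥3% row:** use the recorded Study 1311.5 baseline BSA or the site's ≥3% determination, after checking which of them was transferred.
- **Lower-bound formula:** keep it only as a labelled fallback or sensitivity analysis. Report how many subjects change class in each direction, since recorded BSA and area scores are both estimates.
- **MDA skin item:** state that the separately recorded M16-244 BSA is used. This also covers visits where PASI was not required under footnote u. There a derived BSA would be missing, and a responder with exactly four of the other six items met would become undetermined.

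The cost is SAP wording, some programming and a check of what Study 1311.5 data are held. BSA is already scheduled at M16-244 visits, so no new collection is needed there.
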